2.4 Safety Population

The safety population will include all enrolled patients who have received at least 1 dose of study medication. All patients in the safety population will be analyzed according to the actual treatment received.

All safety analyses will be performed using the safety population.

2.5 Pharmacokinetics Population

The PK population will include enrolled patients with sufficient dosing and PK data to reliably estimate PK parameters as determined by a clinical pharmacologist. The PK population will be used for PK analyses.

2.6 Pharmacodynamics Population

The pharmacodynamics population will include enrolled patients with sufficient dosing and sufficient pharmacodynamics data to reliably measure pharmacodynamics parameters. The pharmacodynamics population will be used for pharmacodynamics analyses.

3. HYPOTHESES AND DECISION RULES

3.1 Statistical Hypotheses

Primary hypothesis to be tested:

The primary null hypothesis is that there is no difference in modified progression-free survival (mPFS) between the 2 treatments of A+AVD and ABVD. The alternative hypothesis is that A+AVD improves mPFS.

Key secondary hypothesis to be tested:

The null hypothesis is that there is no difference in overall survival (OS) between the 2 treatments of A+AVD and ABVD. The alternative hypothesis is that A+AVD improves OS.

Hypotheses for the secondary endpoints will also be tested.

3.2 Statistical Decision Rules

3.2.1 Testing Significance for Primary Endpoint

Modified PFS will be tested at a 1-sided significance level of 0.025. We will conclude that the A+AVD treatment can improve mPFS compared with the ABVD treatment if the test is statistically significant.

3.2.2 Testing Process and Significance for Key Secondary Efficacy Endpoint

Key secondary endpoint will be tested at 1-sided, 0.025 level only when the test of the primary endpoint (mPFS) is statistically significant. If the test is statistically significant, we will conclude that the A+AVD treatment can make improvement in OS compared with the ABVD treatment.

4. INTERIM ANALYSIS

4.1 Interim Analysis

There will be 2 formal interim analyses in this study.

The first formal interim analysis to be performed is a futility analysis. The CR rate at the end of frontline therapy will be analyzed when the first approximately 348 patients have completed the regimen to which they were randomized (ie, received the planned study drug regimen with no more than 2 missed doses of A+AVD or ABVD) or have discontinued treatment prior to completion. Recommendation by the independent data monitoring committee (IDMC) whether to terminate the study based on this interim analysis will be determined upon evaluation of the overall safety information and efficacy data, specifically if the CR rate per independent review facility (IRF) for the A+AVD arm is at least 5% lower than that of the ABVD arm and trends in mPFS and other efficacy endpoints suggest inferior efficacy in the A+AVD arm. This futility analysis does not require adjustment of the type I error.

The second formal interim analysis is for OS to be performed at the time of the final mPFS analysis. Overall type-I error for OS will be controlled using the O'Brien-Fleming method with a Lan-DeMets alpha spending function, with final OS analysis scheduled for when 112 deaths have occurred.

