**Brentuximab vedotin (ADCETRIS®)**

**Clinical Study Protocol C25003 Amendment 7, EudraCT: 2011-005450-60**

information and efficacy data (CR rate per IRF for the A+AVD arm at least 5% lower than that of the ABVD arm, with trends toward inferior A+AVD efficacy for mPFS and other efficacy parameters).

The final analysis of the mPFS primary endpoint will be conducted when 260 mPFS events occur, approximately 2 years after randomization of the last patient; an interim efficacy analysis of OS will also be conducted at that time. The final analysis of OS will be conducted when 112 deaths occur, approximately 4 years after randomization of the last patient.

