#### **3.2 Secondary Endpoints**

The key secondary endpoint is

- OS

Other secondary endpoints are:

- Rate of CR as best overall response achieved at the end of randomized regimen (A+AVD or ABVD) per IRF assessment using the Revised Response Criteria for Malignant Lymphoma
- AEs, SAEs, assessments of clinical laboratory values, and vital sign measurements
- EFS
- DFS
- ORR
- DOR per IRF
- DOCR per IRF
- The rate of patients not in CR that received irradiation
- CR rate per IRF at the end of frontline therapy
- The rate of Cycle 2 PET negativity
- PRO per European Organization for Research and Treatment of Cancer (EORTC) QLQ-C30

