#### **Other Secondary Efficacy Endpoints**

CR per IRF will be analyzed based on the ITT population. CR rate per IRF is defined as the proportion of patients who achieve CR at the end of treatment with randomized regimen (A+AVD or ABVD) as determined by an IRF. CR rates between the 2 treatment arms will be compared using a stratified Cochran-Mantel-Haenszel (CMH) test. A logistic regression model will be used to estimate the treatment effect in terms of odds ratio. The odds ratio and its associated 95% CIs will be presented. Sensitivity analyses for CR per IRF will be performed using the response-evaluable population. CR rate per investigator will also be analyzed similarly using the ITT population.

Comparison of the ORR between the 2 treatment groups will be conducted using the stratified Cochran-Mantel-Haenszel test. The 95% CI of the difference of the response rates

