#### **8.1.10 Interim Analyses**

Two formal interim analyses (IAs) are planned for this study.

The first IA to be performed is a futility analysis. CR rate will be analyzed when the first approximately 348 patients have completed the regimen to which they were randomized (ie, received the planned study drug regimen with no more than 2 missed doses of A+AVD or ABVD) or have discontinued treatment prior to completion.

Recommendation by the IDMC whether to terminate the study based on this IA will be determined upon evaluation of the overall safety information and efficacy data, specifically if the CR rate per IRF for the A+AVD arm is at least 5% lower than that of the ABVD arm, and trends in mPFS and other efficacy endpoints suggest inferior efficacy in the A+AVD arm.

Enrollment will continue during the first IA.

An IA for OS is also planned to occur at the time of the final mPFS analysis. Overall type I error for OS will be controlled using the O'Brien-Fleming method with a Lan-DeMets alpha-spending function.

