5.8.4.3 Complete Remission Rate at the End of Frontline Therapy

CR rate at the end of frontline therapy per IRF is defined as the proportion of patients who achieve CR at the end of frontline therapy as determined by an IRF. CR at the end of frontline therapy is a binary outcome variable.

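### Does the futility rule compare complete remission at two different time points?

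*SAP*

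**What the plan says.** SAP 4.1 sets the first interim analysis, for futility, in one paragraph. It opens with the endpoint: "The CR rate at the end of frontline therapy will be analyzed when the first approximately 348 patients have completed the regimen". It then asks the data monitoring committee (IDMC) to weigh overall safety and efficacy, specifically whether "the CR rate per independent review facility (IRF) for the A+AVD arm is at least 5% lower than that of the ABVD arm" and whether mPFS and other efficacy endpoints also trend against A+AVD. It adds that no type I error adjustment is needed.

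Protocol 8.1.10 gives the same criterion, "specifically if the CR rate per IRF for the A+AVD arm is at least 5% lower than that of the ABVD arm", again without a time point. Its opening sentence on the analysis says only that CR rate will be analysed.

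Two CR endpoints are defined elsewhere:

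- **End of randomised regimen.** Protocol 8.1.6.2 and SAP 5.8.4.2 both state: "CR rate per IRF is defined as the proportion of patients who achieve CR at the end of treatment with randomized regimen". Protocol 3.2 lists this endpoint as "Rate of CR as best overall response achieved at the end of randomized regimen".
- **End of frontline therapy.** Protocol 3.2 lists "CR rate per IRF at the end of frontline therapy". SAP 5.8.4.3 begins its definition: "CR rate at the end of frontline therapy per IRF is defined as the proportion of patients".

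For a patient who switches before finishing A+AVD or ABVD, SAP Table 5-1 places completion of frontline therapy after one alternative regimen.

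**The concern.** The opening sentence of SAP 4.1 points to end-of-frontline CR. The criterion uses a phrase that SAP 5.8.4.2 and protocol 8.1.6.2 define at the end of the randomised regimen. A programmer who looks up that phrase could compute the 5% comparison on a different endpoint from the one just named.

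The timing also looks awkward. Patients count towards the 348 once they complete or discontinue the randomised regimen. A recent switcher may still be on the alternative regimen at that point, with no end-of-frontline assessment. If the frontline reading applies, a CR reached on the physician's alternative is credited to the randomised arm. Table 5-1 also has no row for a patient who misses more than two doses and starts no alternative.

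This is the only planned efficacy look that could end the trial because A+AVD is doing worse. If switching, or CR after switching, differed between arms, the two readings could fall on opposite sides of the threshold.

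**Working it through.** **Reading the passages together.** No sentence in SAP 4.1 gives a second time point. The first names the end of frontline therapy; the criterion adds that the IRF, not the investigator, is the assessor. Together they give the endpoint in SAP 5.8.4.3. The phrase CR rate per IRF is not reserved for the other endpoint. In SAP 5.8.4.2 it is shorthand under a heading that already states the randomised regimen, and in protocol 3.2 those words appear only in the frontline entry. Protocol 8.1.10 leaves the time point open, protocol 8.1 leaves analysis details to the SAP, and SAP 4.1 supplies one.

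**Where the readings differ.** For a patient who completes the randomised regimen without switching, frontline therapy is the randomised regimen and the CR status is the same. Only switchers can differ.

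**Size.** The plan gives no operating characteristics for this rule, so there is no figure of its own to reproduce. Inputs:

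- 348 patients (SAP 4.1) at 1:1 allocation, taken as 174 per arm.
- The 5% read as percentage points: 0.05 × 174 = 8.7, so the CR part is met when A+AVD has at least 9 fewer CRs.
- ABVD CR of 75% at the end of the randomised regimen. This is an assumption; protocol 1.4 cites 72% to 90% for ABVD and BEACOPP.
- Switch rates s_A (A+AVD) and s_B (ABVD), and CR after switching r. The documents give none of these, so all are assumed.

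If switchers were not in CR before the switch, end-of-frontline CR in each arm equals randomised-regimen CR + s × r. The A+AVD minus ABVD difference therefore moves by r × (s_A − s_B). With 5% against 3% this is 0.5 × 0.02 = 1.0 point or 0.8 × 0.02 = 1.6 points, about 2 or 3 patients of 174.

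Exact binomial probability that the CR part is met, with a true 8-point deficit (67% v 75%):

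| Case | r = 50% | r = 80% |
|---|---|---|
| Randomised-regimen CR | 0.740 | 0.740 |
| Frontline CR, 3% switch in each arm | 0.743 | 0.746 |
| Frontline CR, 5% switch in each arm | 0.746 | 0.750 |
| Frontline CR, A+AVD 5%, ABVD 3% | 0.672 | 0.627 |
| Frontline CR, A+AVD 3%, ABVD 5% | 0.808 | 0.844 |

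If half the switchers are still pending and counted as non-CR, or were already in CR before the switch, the gain halves. The last two rows become 0.707 / 0.687 and 0.775 / 0.795.

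With no true deficit (75% v 75%), the randomised-regimen figure is 0.146. With 5% switching in each arm it is 0.137 / 0.131, with 5% against 3% it is 0.096 / 0.071, and reversed it is 0.194 / 0.229.

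**Evidence on switching.** Protocol 6.3.3 and 6.4 permit an alternative frontline regimen only after a Cycle 2 Deauville score of 5. The nearest figure, in protocol 1.3, is a negative Cycle 2 PET in 14 of 15 AVD-cohort patients. One positive in 15 is 7% (exact 95% CI 0.2% to 32%), and that is positivity, not a score of 5. Nothing in the documents points to an imbalance between arms in either direction.

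**The case for a change.** The strongest case for a change is that the one efficacy rule able to stop the trial should have one explicit endpoint, and a few words would provide it. The only sentences that define CR rate per IRF in those words place it at the end of the randomised regimen. The trigger is built on that regimen too. If the SAP means frontline CR, it arguably narrows the protocol's term, yet SAP section 6 declares no change from the protocol.

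Part of this stands: the criterion sentence omits its time point, and the SAP does not say how a switcher with a pending assessment is counted at the cut. The rest is weaker.

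- The trigger fixes when the look happens, not which scan is used. End-of-therapy scans come 3 to 7 weeks after the last dose of frontline therapy, so some completers are also pending when the count is reached, under either reading.
- Under protocol 4.1, a patient with a score of 5 takes the alternative for what remains of planned frontline treatment, and so need not finish long after others.
- The rule in SAP 5.8.4.2 that nonevaluable patients count as non-CR does not mention pending patients in an interim subset. Applying it to them is inference.
- Scans in the Schedule of Events (footnotes j and k) are tied to the last dose of frontline therapy, which gives an early stopper an assessment time even though Table 5-1 has no row for that patient.
- Protocol 8.1.10 states no time point, so there is no clear departure for SAP section 6 to declare.

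Preferring randomised-regimen CR because it isolates the assigned drugs is a reasonable view. But protocol 4.1 does not count a switch as an mPFS event, and the non-CR component of mPFS is judged after frontline therapy. Frontline CR therefore matches the primary endpoint. Statisticians could differ on this, and that does not make the named endpoint wrong.

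**Conclusion.** The concern does not hold as an inconsistency. Followed as written, SAP 4.1 yields CR at the end of frontline therapy per IRF, as defined in SAP 5.8.4.3, and that is a coherent choice for this look. What remains is a time point left out of one sentence and an unstated convention for pending switchers. Both are details that the analyst and the IDMC can settle when specifying the interim tables; the IDMC charter, which is not among the documents, may already do so.

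With equal switching of up to 5% per arm, the choice of reading moves the chance of meeting the CR part by about one point (74% to at most 75%) with an 8-point deficit, and by less than two points (15% to 13%) with none. The wider range with the deficit, 63% to 84%, comes entirely from an assumed 5% against 3% imbalance with 50% to 80% CR after switching. All these figures assume 174 per arm and 75% CR on ABVD. They describe one part of a rule that also needs adverse mPFS and other efficacy trends and leads only to a recommendation, so they show no change in the stopping decision. Type I error is unaffected. No change to the plan follows.

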4.2 Independent Data Monitoring Committee (IDMC)

An IDMC will review safety and efficacy data at the interim analyses. The IDMC will provide a recommendation regarding study continuation based on the safety and efficacy parameters. In the event that the study is terminated early based on an IDMC recommendation, Millennium will notify the appropriate regulatory authorities. Detailed information regarding the composition of the IDMC and detailed IDMC procedures will be provided in the IDMC charter.

The first formal safety review will occur after the first 100 patients have completed 2 cycles (8 weeks) of treatment or discontinued prior to completing 2 cycles of treatment. Subsequently, IDMC safety reviews will be performed periodically per the IDMC charter.

5. STATISTICAL METHODOLOGY

In general, summary tabulations will be presented that display the number of observations, mean, standard deviation, median, minimum, and maximum for continuous variables, and the number and percent (of non-missing) per category for categorical data, unless specified otherwise.

5.1 Sample Size Justification

The primary endpoint of the study is mPFS, and the study is powered on the following assumption: a 2-year mPFS of 81% for patients in the A+AVD treatment group versus 73% for patients in the ABVD treatment group (HR = 0.67, assuming an emergent plateau in the PFS event rate after 2 years). A total of 260 mPFS events will provide 90% power to detect a hazard ratio of 0.67 at a 1-sided significance level of 0.025 using a log-rank test.

Approximately 1240 patients will be randomized to achieve (with 95% probability) 260 mPFS events in about 60 months assuming 36 months of accrual, a 5% annual dropout rate, and 24 months of mPFS follow-up after last patient in.

5.2 Randomization and Stratification

The randomization scheme will be generated by Millennium. Prior to dosing, a randomization number will be assigned to each patient. The randomization schedule also includes the study specific identifiers (company name, protocol name, and protocol number) and the date and time the schedule was generated.

Patients will be randomized in an overall ratio of 1:1 to A+AVD or ABVD. Patients will be stratified by region (Americas versus Europe versus Asia), and number of IPFP risk factors (0-1 versus 2-3 versus 4-7).

5.3 Unblinding

This is an open-label study; investigators and patients will know the individual treatment assignments. However, aggregate efficacy data will be blinded to the sponsor's study team, investigators, and patients throughout the study conduct. The IRF will be blinded to treatment assignments.

5.4 Data Handling

5.4.1 Methods for Handling Missing Data

All available efficacy and safety data will be included in data listings and tabulations. Data that are potentially spurious or erroneous will be examined under the auspices of standard data management operating procedures.

In general, missing data will be treated as missing and no data imputation will be applied, unless otherwise specified. For Quality of Life Data, missing elements may be substituted with the average of non-missing items per published methods of analysis.

Last observation carried forward method and multiple imputation method may be considered for some clinical outcomes as deemed appropriate.

5.4.1.1 Missing/Partial Dates in Screening Visit

The following rules apply to dates recorded in the screening visits, with the exception of prior therapies (Section 5.4.1.2).

- If only the day-component is missing, the first day of the month will be used if the year and the month are the same as those for the first treatment. Otherwise, the 15th will be used.
- If only a year is present, and it is the same as the year of the first treatment, the 15th of January will be used unless it is later than the first treatment, in which case the date of the first of January will be used.
- If only a year is present, and it is not the same as the year of the first treatment, the 15th of June will be used, unless other data indicates that the date is earlier, in which case the 15th of January will be used. .

5.4.1.2 Missing/Partial Dates in Adverse Events/Concomitant Therapies/Subsequent Therapies

Every effort will be made to avoid missing/partial dates in on-study data. If the resolution date of a resolved adverse event (AE) or the stop date of a concomitant therapy is missing, the following rules are to be used unless conflicting data exists: if month and year are present and the day of the month is missing, the last day of the month is imputed. If only a

Brentuximab vedotin (ADCETRIS™)
Statistical Analysis Plan, Study C25003

year is present, the 31st of December is used. After imputation, the imputed dates will be compared against the date of death, if available. If the date is later than the date of death, the date of death will be used as the imputed date instead.

In cases where the onset date of an adverse event is completely or partially missing, the following imputation rules will be used:

1. When month and year are present and the day of the month is missing,
 - If the onset month and year are the same as the month and year of first treatment with study drug, the day of first treatment or the day-component of the resolution date are imputed, whichever is earliest.
 - If the onset month and year are not the same as the month and year of first treatment with study drug, the first day of the month is imputed.
2. When only a year is present, or no components of the onset date are present,
 - If the resolution date is available, the earlier of the resolution date (possibly imputed) and the date of first treatment will be used.
 - If the resolution date is missing, and the onset-year is the same as the year of first treatment with study drug, then the date of first treatment with study drug is used.
 - Otherwise if only a year is present, the 1st of January of that year is imputed.
3. If none of the previous rules can be applied, then the date of first treatment with study drug is imputed as the onset date.

The imputation rules for missing/partial start dates of concomitant therapies will be the same as the above with the exception as follows:

For prior therapy data, no imputation will be done for start dates.

The imputation rules for missing/partial start dates of subsequent therapies recorded as concomitant medications will be the same as the above with exceptions as follows.

1. When month and year are present and the day of the month is missing,

Brentuximab vedotin (ADCETRIS™)
Statistical Analysis Plan, Study C25003

- a. If the month and year of the start date are the same as the month and year of treatment termination, the day of treatment termination or the day-component of the stop date is imputed, whichever is earliest.
 - b. If the start month and year are not the same as the month and year of treatment termination, the first day of the month is imputed.
2. When only a year is present, or no components of the start date are present, the date will not be imputed.

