### **10.3 Monitoring of Adverse Events and Period of Observation**

AEs, both nonserious and serious (which include all deaths), will be monitored throughout the study as follows:

- AEs will be reported from first dose of frontline therapy through 30 days after administration of the last dose of frontline therapy and recorded in the eCRFs. A diagnosis of a malignancy other than classical HL that occurs at any time prior to study closure must be recorded in the eCRF regardless of causality. Additionally, events of malignancy occurring more than 30 days post the last dose of frontline therapy that are deemed serious and related to study drug must be reported to Millennium Department of Pharmacovigilance & Risk Management or designee on an SAE form. All events relating to peripheral neuropathy, regardless of seriousness, will be followed for all changes in severity until resolution to baseline or study closure, whichever occurs first, and recorded in the eCRF.

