5.11.1 Adverse Events

Treatment-emergent adverse events are defined as any AE that occurs after administration of the first dose of study drug and through 30 days after the last dose of frontline therapy.

The MedDRA dictionary will be used to code the investigator's adverse event terms.

Adverse event tables will summarize subject incidence by treatment group actually received.

The severity of adverse events will be assessed using NCI CTCAE version 4.03.

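### A resolved adverse event whose onset is recorded only as a year after the year of first treatment is dated at first treatment, although the recorded year rules that date out

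*SAP*

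**What the plan says.** SAP Section 5.4.1.2 gives numbered rules for incomplete adverse event onset dates. Rule 2 opens with "When only a year is present, or no components of the onset date are present" and has three bullets.

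- First bullet: when there is a resolution date, "the earlier of the resolution date (possibly imputed) and the date of first treatment will be used".
- Second bullet: "If the resolution date is missing, and the onset-year is the same as the year of first treatment with study drug", the date of first treatment is used.
- Third bullet: "Otherwise if only a year is present, the 1st of January of that year is imputed".

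The same section fills in incomplete resolution dates beforehand. If only the year of resolution is known, "the 31st of December is used", subject to a cap at the date of death. A year-only resolution is therefore enough to trigger the first bullet.

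SAP Section 5.11.1 defines treatment-emergent events as those after the first dose and "through 30 days after the last dose of frontline therapy". Protocol Section 10.3 keeps one kind of event open for much longer: "A diagnosis of a malignancy other than classical HL that occurs at any time prior to study closure" must be entered in the eCRF regardless of causality.

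**The concern.** The second and third bullets look at the recorded year, but only when the resolution date is missing. The first bullet never looks at it. Two events with the same recorded later year are therefore dated years apart merely because one of them resolved. Knowing more about an event makes its onset date worse.

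What is at stake is membership of the treatment-emergent tables in SAP Sections 5.11.1.1 and 5.11.1.2. A late second malignancy that the recorded year places outside the window could be tabulated as if it began on the first day of treatment.

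**Working it through.** No figure in the documents depends on this rule, so there is nothing to reproduce. The check follows the rule through by date.

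**Inputs.** The three bullets and the 31 December rule come from SAP 5.4.1.2, and the window from SAP 5.11.1. Planned treatment is six 28-day cycles with doses on Days 1 and 15 (Protocol 4.1 and 4.3). The calendar dates below are illustrative.

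**Window length.** The last planned dose falls 5 × 28 + 14 = 154 days after the first. The window closes 154 + 30 = 184 days after the first dose. Delays or a switch to another frontline regimen would lengthen it.

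**General argument.** Let F be the first-dose date, R the resolution date, Y the recorded onset year and W the end of the window.

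1. If Y is later than the year of F, then F < 1 January Y ≤ R. The first bullet gives min(R, F) = F in every case. A grid of 365 first-dose days in 2013, five onset years (2014 to 2018) and 53 weekly resolution dates within each onset year confirms it: 365 × 5 × 53 = 96,725 cases, and all 96,725 receive the first-dose date.
2. If 1 January Y ≤ W, the window reaches into year Y. The first bullet gives F and a year check gives 1 January Y. Both lie inside the window, so status is the same.
3. If 1 January Y > W, every day of year Y lies after the window. The event cannot be treatment-emergent, yet the first bullet dates it at F.

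**Worked cases.** First dose 4 March 2013, last planned dose 5 August 2013, window to 4 September 2013. The year check is the change proposed below.

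| Recorded onset | Resolution | Rule 2 as written | With year check |
|---|---|---|---|
| 2015 | 20 Sep 2015 | 4 Mar 2013, inside | 1 Jan 2015, outside |
| 2015 | 2015 only, so 31 Dec 2015 | 4 Mar 2013, inside | 1 Jan 2015, outside |
| 2015 | none | 1 Jan 2015, outside | 1 Jan 2015, outside |
| 2013 | 1 Jun 2013 | 4 Mar 2013, inside | 4 Mar 2013, inside |
| 2012 | 1 May 2013 | 4 Mar 2013, inside | 1 Jan 2012, outside |
| 2012 | 15 Jan 2013 | 15 Jan 2013, outside | 1 Jan 2012, outside |

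The first and third rows differ only in whether the event resolved. The fifth row shows the same bullet overriding an earlier recorded year. That case should be rarer still, because adverse events are collected from the first dose.

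**A patient whose window crosses the year end.** First dose 1 November 2013, last planned dose 4 April 2014, window to 4 May 2014, onset recorded as 2014, resolved later that year. Rule 2 gives 1 November 2013 and the year check gives 1 January 2014. Both are inside the window, so only the date is wrong.

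**Possible rescue in the text.** The exception for conflicting data in SAP 5.4.1.2 is attached to resolution and stop dates, not to onset dates. No other provision protects the recorded year.

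**The case against.** The strongest reply is that the effect is too small to matter. A wrong status needs several things together: onset after the window, only a year recorded, and a resolution date, actual or imputed. An unresolved malignancy keeps its year under the third bullet. The SAP intends partial dates to be avoided, and Protocol Section 11.2 has monitors pursue missing data. Late serious events and deaths are listed whatever their treatment-emergent status (SAP 5.11.1.2 and 5.11.1.3). The rule is the same in both arms and errs towards counting more harm. All of this stands, and it keeps the point minor.

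What does not stand is a defence of the rule as cautious. For a recorded later year, 1 January is the earliest possible onset. A year check therefore loses no event that could be treatment-emergent. The only later-year events that the present rule adds are those that the recorded year excludes.

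A reader might also infer more than the documents support:

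- That onset-time or duration results for adverse events would be distorted. Neither document plans such an analysis. The planned outputs are incidence tables and listings.
- That late neuropathy is caught in the same way. Protocol Section 10.3 follows neuropathy events for changes in severity up to study closure, but general adverse event reporting ends 30 days after the last frontline dose. A new neuropathy starting years later is not clearly collected, and one that began within the window is treatment-emergent anyway.
- That the problem is common because many treatment windows span a 31 December. In those patients a next-year onset can lie inside the window, and status does not change, as the second example shows.

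**Conclusion.** The point holds as a minor defect in a stated rule. Every resolved event with a year-only onset in a year after first treatment gets the first-dose date, against its own record. Among these later-year events, treatment-emergent status is demonstrably wrong only where the recorded year lies wholly after the window.

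This rests on three assumptions:

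- An onset on the first-dose date counts as treatment-emergent. The SAP says only that the event occurs after the first dose is given, but its habit of imputing to that date suggests that Day 1 is included.
- A late malignancy is held as an adverse event record. Protocol Section 10.3 places the requirement among its adverse event reporting rules but does not name the eCRF page.
- Year-only onsets occur at all. The documents give no frequency. If 0.1% to 1% of adverse event records are assumed to have one (1 to 10 per 1,000 records), only the resolved, post-window subset of those changes status, so few events are likely to be affected.

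The primary endpoint, overall survival, type I error and sample size are unaffected.

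**What to change.** In SAP 5.4.1.2, onset rule 2, restrict the first bullet to onsets with no recorded year or with the same year as first treatment. For any other recorded year, impute 1 January of that year whether or not a resolution date exists, capped at the resolution date. The cap matters only if the recorded dates conflict, with resolution before the onset year. State in SAP 5.11.1 whether an imputed onset on the first-dose date counts as treatment-emergent.

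The cost is one or two sentences and one extra programming condition. Dates for onsets with no year, or in the year of first treatment, do not change. Start dates of concomitant therapies follow the same rules by reference, so the revised wording should be checked for them too.
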